RICAZA study Investigators conducted a study using subcutaneous azacitidine in 27 AML patients who had undergone reduced-intensity conditioning (RIC) allogeneic stem cell transplantation (19). The conditioning regimen was fludarabine, melphalan, and alemtuzumab, and the azacitidine regimen consisted of 36 mg/m2 for 5 consecutive days every 28 days for up to 10 cycles. The median time to start of azacitidine treatment was 64 days after the allogeneic stem cell transplantation. An additional 19 patients enrolled as the control group, received the same conditioning regimen, but no maintenance therapy. The investigators found that 3 of the 27 patients who received maintenance therapy developed grade 2 acute GVHD, and none developed grade 3e4 GVHD. Two patients developed limited chronic GVHD of the skin, and none developed chronic extensive GVHD. In comparison, the control group had a higher GVHD rate, with 7 of 19 developing grade 2 acute GVHD and 7 of 19 chronic GVHD. Despite these encouraging results, 7 of the 27 patients relapsed at a median of 6 months after transplantation.

Decitabine is another epigenetic therapy that has been investigated in the post-transplant maintenance setting (20). The maximum tolerated dose (MTD) was defined as the maximum dose at which $\leq 25\%$ of people experience dose-limiting toxicities during the first cycle of treatment. Twenty-four patients were enrolled and 22 were evaluable. All 4 dose levels were completed and no MTD was reached. Overall, decitabine maintenance was well tolerated. Grade 3 and 4 hematological toxicities were experienced by 75% of patients, including all patients treated at the highest dose level. Nine patients completed all 8 cycles and 8 of them remain in CR. Nine patients died from relapse (n = 4), infectious complications (n = 3), and GVHD (n = 2). Most occurrences of acute GVHD were mild and resolved without interruption of treatment; 1 patient died of acute gut GVHD. In conclusion, decitabine maintenance is associated with acceptable toxicities when given in the post-allo transplantation setting.

Despite the encouraging results reported, pre-emptive strategies, to prevent relapse, including pharmacological, immunological and cellular therapies pose the dilemma of administering potentially toxic therapy without evidence of relapse. Therefore patient selection for the right group of patients to be included in those studies is very important.

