.05	.82	8 8 20
.10	.54	8 20 25
.15	.32	8 25 25
.20	.18	25 25 25

Patients who have relapsed (REL). In this subgroup, response will be defined as disease remission at any time point within the first 6 cycles of therapy with SGI-110. Otherwise, the same design as that used in the MRD subgroup will be used.

7.2. High Risk Patients. This cohort will include high risk patients with one-year relapse incidence of 35%-45%. They will receive maintenance therapy with SGI for one year. A maximum of 40 patients will be enrolled. The primary endpoint for this cohort will be relapse-free survival (RFS) time. The Bayesian method of Thall et al will be used to monitor RFS time in this cohort (41). We denote the standard historical therapy by S and the experimental SGI-110 therapy by E. We assume that TS=time to disease progression or death in this cohort associated with standard therapy follows an exponential distribution with median mS and that TE=time to disease progression or death in these patients associated with the experimental SGI-110 therapy follows an exponential distribution with median mE. We denote the median RFS times for the standard and experimental therapies by mS and mE, respectively. Under a Bayesian model, both mS and mE are assumed to follow Inverse Gamma (a, b) priors, denoted IG(a, b). From historical data, Pr(TS > 12 months) = .35, which implies that the historical median RFS = 7.9 months in this group under the assumption of exponentially distributed RFS times. For priors, we assume that $mS \sim IG$ (17.6, 131.2), which has mean = 7.9 months and variance = 4.0 months. We assume that mE ~ IG (3, 15.8), which has the same mean = 7.9months but a much larger variance = 62.4. We will monitor possibly right-censored TE continuously through the trial and will terminate accrual to this cohort if at any time:

$$Pr(mS < mE \mid data) < 0.07.$$

The accrual rate in this cohort is expected to be 2 patients per month. We will follow patients until all patients in the cohort have been followed for two years after transplant. We will enroll a maximum of 40 patients in this cohort.

Operating Characteristics. The operating characteristics of this stopping rule under the assumptions above were obtained by simulating the trial 2000 times each using the program One-Arm TTE v 3.0.6. These are summarized the table below.

Operating Characteristics of the Stopping Rule for Maintenance Patients

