True Median RFS (months)	True Pr (RFS > 12 months)	Pr (Stop Early)	Mean Sample Size
4.4	.15	.827	21.8

6.0	.25	.339	32.5
7.9	.35	.103	37.3
10.4	.45	.036	39.0
13.9	.55	.009	39.7

Secondary outcomes. Secondary outcomes will include disease-free survival (DFS) time, relapse free survival (RFS), overall survival (OS) time, graft-versus-host disease, safety and duration of remission. Within each subgroup, these events will be tabulated and the distributions of RFS and OS time estimated using the method of Kaplan and Meier (42).

7.3 Cross-over. Patients treated on cohort #2 (patients with minimal residual disease while in morphological remission and cohort #3 (maintenance treatment cohort) will be allowed to receive higher doses of SGI-110 if they progress while on therapy with the study drug. Patients who are considered for cross-over to another study cohort due to progression of disease with an aim to receive higher doses of SGI-110 will be screened for the eligibility of that study cohort prior to initiation of higher doses of study drug. The subgroup of cross-over patients will be followed for evaluation of subsequent outcomes, such as response OS, starting from the date of cross-over.

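### Cohort 3 has no cohort-level rule on toxicity or death without relapse, and its one accrual rule pools progression with death, so fewer relapses can offset more deaths

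*Combined protocol and SAP*

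**What the plan says.** Cohort 3 takes high-risk patients in morphological remission with no detectable residual disease (3.1.4.3) and allows up to 12 cycles (4.2.3.6). Section 7.2 sets one accrual rule: stop if Pr(mS < mE | data) < 0.07. The monitored time is defined so that "TE=time to disease progression or death in these patients associated with the experimental SGI-110 therapy follows an exponential distribution with median mE". Under 6.3.3, progression includes the return of residual disease as well as morphological relapse.

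The benchmark is "From historical data, Pr(TS > 12 months) = .35", and the population is described thus: "This cohort will include high risk patients with one-year relapse incidence of 35%-45" percent. The table of operating characteristics is indexed by pooled RFS alone.

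On safety, 7.2 states: "Secondary outcomes will include disease-free survival (DFS) time, relapse free survival (RFS), overall survival (OS) time, graft-versus-host disease, safety and duration of remission". These events are to be tabulated, and no limit is attached to them. Toxicity otherwise acts patient by patient, through dose modification (4.4) and discontinuation of treatment, which includes severe GVHD (8.4). Section 4.4.2.3 keeps infections out of drug-related toxicity for dose modification.

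Section 2.0 says that preventive strategies "pose the dilemma of administering potentially toxic therapy without evidence of relapse". Of the decitabine maintenance study it reports: "Nine patients died from relapse (n = 4), infectious complications (n = 3), and GVHD (n = 2").

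**The concern.** A rule on total failures cannot tell a relapse from a toxic death. If the drug prevents relapses and also causes deaths without relapse, the rule sees only the net effect. Severe toxicity that is not fatal does not enter it at all.

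This matters most in cohort 3, whose patients have no detectable disease when treatment starts. The background section itself names toxicity in such patients as the dilemma. In the decitabine study it cites, 5 of the 9 deaths (3 infection, 2 GVHD) were not from relapse. At stake is whether all 40 patients could be enrolled while death without relapse rises well above its historical level, with no pre-stated point at which accrual is reviewed.

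Cohorts 1 and 2 also lack a separate toxicity limit: 7.1 monitors response for futility only. The mechanism differs there, because treatment stopped for severe toxicity before remission counts as a non-response.

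**Working it through.** **1. Inputs from section 7.2.** Priors: mS ~ IG(17.6, 131.2) and mE ~ IG(3, 15.8). Cutoff 0.07, 2 patients per month, maximum 40.

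**2. Priors and benchmark.** For IG(a, b), the mean is b/(a − 1) and the variance is mean²/(a − 2).
- mS: 131.2/16.6 = 7.90; 7.90²/15.6 = 4.00.
- mE: 15.8/2 = 7.9; 7.9²/1 = 62.4.
- Median at 12-month RFS .35: 12 × ln 2/(−ln .35) = 7.92 months. Total hazard: −ln(.35)/12 = 0.0875 per month.

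All agree with the plan.

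**3. The plan's table.** With d events, mE | data ~ IG(3 + d, 15.8 + ln 2 × total follow-up). The rule was simulated with Poisson accrual and a look at each arrival, 20,000 runs per row.

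| True 12-month RFS | Median (months) | Printed Pr(stop) | Simulated | Full accrual (1 − printed) |
|---|---|---|---|---|
| .15 | 4.4 | .827 | .827 | .173 |
| .25 | 6.0 | .339 | .344 | .661 |
| .35 | 7.9 | .103 | .095 | .897 |
| .45 | 10.4 | .036 | .028 | .964 |
| .55 | 13.9 | .009 | .008 | .991 |

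The table reproduces. Stopping becomes more likely than not only below a 12-month RFS of about .215 (median about 5.4 months). That is a total hazard of −ln(.215)/12 = 0.128, or 1.46 times the historical 0.0875.

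**4. Implied split (derived, not stated in the plan).** One-year failure is 1 − .35 = .65. With relapse at 35% to 45%, death without relapse is 30% to 20%. The midpoint is 40% and 25%. With constant cause-specific hazards:
- relapse: 0.0875 × 40/65 = 0.0538 per month
- death without relapse: 0.0875 × 25/65 = 0.0337 per month

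**5. Exact cancellation.** Halve the relapse hazard (0.0269) and multiply the death hazard by 1.8 (0.0606). The total is again 0.0875, so RFS stays at .35. One-year relapse is .65 × 0.0269/0.0875 = 20%, and death without relapse is 45%. The 7.9-month row applies: stop .103, full accrual .897. Using that row's mean sample size of 37.3, deaths without relapse within 12 months are:
- historical: 37.3 × .25 = 9.3
- scenario: 37.3 × .45 = 16.8

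If historical relapse is 35% or 45% instead, halving it at unchanged RFS gives .65 − .175 = 47.5% or .65 − .225 = 42.5% death without relapse. The stopping probability is the same.

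**6. When the effects do not cancel** (simulated; range for historical relapse 35% to 45%).

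| Relapse hazard | Death hazard | Pr(stop) | Range |
|---|---|---|---|
| halved | ×2 | .13 | .22 to .08 |
| halved | ×3 | .50 | .70 to .28 |
| unchanged | ×2 | .40 | .50 to .34 |
| unchanged | ×3 | .80 | .89 to .66 |

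**7. Effect of a separate monitor (illustration only).** Add a second monitor on death without relapse, in the same form and with the same 0.07 cutoff. Centre it on a cause-specific median of ln 2/0.0337 = 20.6 months, with the plan's prior shapes rescaled to that mean. In the step 5 scenario, the probability that either rule stops accrual rises from about .10 to about .65. At historical rates it rises from about .10 to about .155.

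**The case against.** Deaths do count as events in the monitored time, so the rule is not blind to them. Three stronger statements that a reader might infer are not supported:

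- *Any relapse benefit hides toxic deaths.* A benefit hides them fully only if it is at least as large as the excess death hazard. With relapse halved and the death hazard tripled, the rule still stops about half of trials.
- *The plan's table shows that a too-toxic maintenance usually reaches full accrual.* The table contains no toxicity scenario, and its worst row stops 82.7%. Linking it to toxicity needs the assumed split in step 4.
- *Cohort 3 has no toxicity trigger.* Patient-level triggers exist in 4.4 and 8.4, and serious events go to the company, the IND Office, the review board and FDA (8.3, 8.5). What is absent is a rule for the cohort.

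It can also be said that trading relapses for deaths at equal or better RFS is acceptable on the chosen primary endpoint. That is a value judgement the sponsor may make, but the plan does not make it openly, and it calls safety a secondary objective without saying when it would interrupt accrual.

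Finally, some front matter was removed and the appendices were not supplied, so a monitoring board described there cannot be excluded. This limits the claim to the supplied text. It does not turn the pooled rule into a safety rule.

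**Conclusion.** The point holds in a limited form. The supplied text has no cohort-level toxicity or non-relapse-death rule for cohort 3, and its single accrual rule lets fewer relapses offset more deaths. From the plan's own figures, full accrual follows in 89.7% of trials when the two cancel, and in 66.1% when there is net harm at a median of 6.0 months. Large net harm is usually caught.

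The count of about 17 against about 9 deaths without relapse rests on three assumptions: constant hazards, the split implied by 35%–45% relapse with RFS .35, and relapse in that figure meaning the same as progression in 6.3.3. The 89.7% and 66.1% do not depend on the split. This is a worthwhile improvement to a design that otherwise performs as printed.

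**What to change.** Add to 7.2 a second accrual monitor for cohort 3 on death without relapse, kept apart from progression, in the Bayesian form the plan already uses. A time-to-event version uses censored follow-up, so accrual need not wait. With a fixed 6-month window at 2 patients per month, about 12 recent patients would be unevaluated at each look.

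The sponsor should set the cutoff and the reference rate, the latter over the same time window as the monitored event. The cited decitabine study's 5/24 = 21% should not serve as a 6-month rate: section 2.0 gives no follow-up time for those deaths, and they span four dose levels.

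Print joint operating characteristics for both rules by relapse and non-relapse-death scenario, including relapse reduced with deaths raised at unchanged RFS. If a monitoring board already exists, 7.2 should refer to it and state what it reviews for this cohort.

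The cost is protocol wording and one table. Deaths are already collected, so no new data are needed. The downside is a modestly higher chance of an unneeded pause at historical rates, put at about .155 against about .10 in the illustration.

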2.0 Background

Relapse is the major cause of treatment failure after allogeneic hematopoietic transplantation for AML or MDS (1, 2) and is associated with a dismal prognosis (3). Treatment options for those patients are mainly restricted to chemotherapy, donor lymphocyte infusion (DLI) or second allo-HSCT(4-7). However, remission induction by chemotherapy is challenging because of low response rated and high toxicity (4).

A promising strategy is administration of hypomethylating agents with donor lymphocyte infusion to augment graft-vs-leukemia effects. Hypomethylating agents have direct antileukemia effects and may also favorably modulate GVL activity. We and others have reported the activity of 5-Azacytidine for relapse after allo-HSCT(8). Recently, the safety of 5-Azacytidine in combination of DLI as first salvage therapy for relapse after allo-HSCT in AML/MDS patients have been shown (9).

SGI-110 is a promising agent for AML and MDS The active metabolite of SGI-110, a dinucleotide, is decitabine. SGI-110 is resistant to modification by cytidine deaminase, a

common pathway of decitabine metabolism and deactivation. Therefore SGI-110 delivers decitabine with a 4-fold longer decitabine half-life and overall exposure up to 8 hours. Initial studies have demonstrated relatively high response rates compared to azacitidine and decitabine. In a phase I study, biologically effective dose (BED) was determined to be 60 mg/m2 Days 1-5. A recent phase II study in relapsed/refractory or treatment naïve older AML patients, overall response rate (including CR+CRp+CRi) was 25.6% and 29.8% in 60 mg/m2 and 90 mg/m2 dose groups respectively. These early results confirmed the clinical efficacy of SGI-110 in AML patients. There has been data that hypomethylating agents may increase the immunogenicity of AML blasts by re-expression of important antigens(10-12). Furthermore, animal studies suggest an immunomodulatory role of hypomethylating agents that might attenuate GVHD after DLI(12, 13).

Early intervention is important for treatment of relapse post transplant. The best opportunity to improve outcomes would be to identify relapsing patients with minimal residual disease (MRD) which has been shown to predict impending hematologic relapse(14, 15).

In the current study, we aim to investigate the use of SGI-110 in combination with DLI for morphologic relapse and presence of MRD in the post allo-HSCT setting.

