- 4.2.2.7 Treatment with SGI-110 will be stopped at any time point if patients exhibit evidence of treatment failure, disease progression, experience of unacceptable toxicity, or the investigator determines that the discontinuation of treatment is in the patient's best interest as provided in Section 6.0.
- 4.2.3. Cohort 3: High risk AML and MDS patients who are in complete remission morphologically with no evidence of minimal residual disease by flow cytometry or cytogenetic or molecular testing after allogeneic stem cell transplantation.
 - 4.2.3.1 The enrolled patients will start treatment at the dose level -1 which is 30 mg/m2 SC daily, days 1 to 5 for each 28-day treatment cycle.
 - 4.2.3.2 Treatment delays up to 70 days will be allowed.
 - 4.2.3.3 The response assessments will be performed per departmental guidelines which is day +100, 6th month, 1- year after allogeneic stem cell transplantation.
 - 4.2.3.4 Disease assessment can be done at any time point after transplantation if it is deemed indicated by the treating physician and/or principal investigator.
 - 4.2.3.5 The dose level of SGI-110 can be increased at least one dose level at the discretion of treating physician and principal investigator if deemed in the best interest of the patient by the treating physician and/or principal investigator.
 - 4.2.3.6 For patients who remain in remission without detectable minimal residual disease at study entry, treatment with SGI-110 will be continued until treatment failure or for a maximum of 12 cycles.
 - 4.2.3.7 Treatment with SGI-110 will be stopped at any time point if patients exhibit evidence of treatment failure, disease progression, experience of unacceptable toxicity, or the treating physician and/or principal investigator determines that the discontinuation of treatment is in the patient's best interest as provided in Section 6.0.
- 4.2.4 **Cross-over.** Patients treated on cohort #2 (patients with minimal residual disease while in morphological remission and cohort #3 (maintenance treatment cohort) will be allowed to receive higher doses of SGI-110 if they progress while on therapy with the study drug. Patients who are considered for cross-over to another study cohort due to progression of disease with an aim to receive higher doses of SGI-110 will be screened for the eligibility of that study cohort prior to initiation of higher doses of study drug.
- 4.3 SGI-110 Reconstitution and Administration

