5.2 Evaluations prior to DLI administration

To be done within 72 hours of each cycle and if clinically indicated, on the third day of each cycle and once in the second and third week: CBC, differential, platelet, SGPT, bilirubin, creatinine, electrolytes.

5.3 Response Evaluation:

Disease status evaluations follow standard practice. If clinically indicated, these studies may be done at other time points, which can replace the nearest planned time point.

For cohorts 1 and 2:

- 5.3.1 To be done after 2nd, 4th, and 6th cycles of SGI-110.
- 5.3.2 After the patients are documented to achieve response, further disease status evaluation will be performed when it is clinically indicated.
- 5.3.3 Disease status will include:
 - 5.3.1.1 Bone marrow aspirate and biopsy with cytogenetics, FISH, flow and molecular studies.
 - 5.3.1.2 Chimerism studies from peripheral blood
- 5.3.4 If a patient shows no evidence of response in the absence of disease progression after the second cycle of SGI-110 (Day 28 +/-7 days), further bone marrow aspirate and/or biopsy will be scheduled to document response at the end of Cycle 4 (Day 28 +/-7 days).
- 5.3.5 If a patient shows no evidence of response in the absence of disease progression even after the fourth cycle of SGI-110 (Day 28 +/-7 days), further bone marrow aspirate and/or biopsy will be scheduled to document response at the end of Cycle 6 (Day 28 +/-7 days).
- 5.3.6 If the patient does not show evidence of response at the end of Cycle 6, the patient

- will be taken off the study with no further follow-up.
- 5.3.7 Bone marrow evaluations and peripheral blood chimerism studies can be ordered more frequently if clinically indicated.

For cohort 3:

- 5.3.8 Disease status evaluations follow standard practice with day +100, Month 6, and 1-year disease evaluations.
- 5.3.9 Disease status evaluation will include:
 - 5.3.9.1 Bone marrow aspirate and biopsy with cytogenetics, FISH, flow and molecular studies.
 - 5.3.9.2 Chimerism studies from peripheral blood.
- 5.4 Outside Physician Participation During Treatment

This will be performed only after the patients are documented to show evidence of response with the therapy (morphological CR for cohort 1 and MRD negative status for cohort 2 respectively). DLI administrations will only be performed at MDACC.

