5.5 Follow-Up Evaluations

Follow-Up evaluations will be performed per AML or MDS standard of care as appropriate.

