 - 6.3.3 For cohort 3, any disease progression with either morphological relapse and/or

evidence of minimal residual disease with flow-cytometry, cytogenetics or molecular testing.

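### Cohort 3's stop-probability table treats every event as known on the date it occurs; the plan's three-marrow schedule does not generally deliver those probabilities, and the direction of the error depends on a counting convention the plan does not state

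*Combined protocol and SAP*

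**What the plan says.** Section 7.2 defines TE as time to progression or death, exponential with median mE, and states: "We will monitor possibly right-censored TE continuously through the trial and will terminate accrual to this cohort if at any time" Pr(mS < mE | data) falls below .07. The table beneath it comes from 2,000 simulated trials under those assumptions.

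Section 6.3.3 defines progression in cohort 3 as morphological relapse and/or "evidence of minimal residual disease with flow-cytometry, cytogenetics or molecular testing". Patients enter with no detectable MRD (3.1.4.3).

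Section 4.2.3.3 sets response assessments at "day +100, 6th month, 1- year after allogeneic stem cell transplantation". Section 5.3.8 agrees: "Disease status evaluations follow standard practice with day +100, Month 6, and 1-year disease evaluations". Anything further is optional or left to routine care: "Disease assessment can be done at any time point after transplantation if it is deemed indicated by the treating physician and/or principal investigator" (4.2.3.4), and "Follow-Up evaluations will be performed per AML or MDS standard of care as appropriate" (5.5). The tests around each cycle in 5.1 are blood counts and chemistry.

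No section says from which date TE runs, how an event found at a marrow is dated, or to what date an event-free patient is counted at a look.

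**The concern.** MRD progression is silent until someone tests for it. The two later gaps between scheduled marrows are about 3 and 6 months, so an MRD event can go unseen for months while the rule is being applied. The plan's own background describes "minimal residual disease (MRD) which has been shown to predict impending hematologic relapse", so it is unlikely that no events come to light through MRD first.

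The posterior uses two sums, the number of events and the total follow-up time. The marrow schedule affects both, and how it does so depends on the missing convention. This is the only numerical stopping rule for cohort 3, and the table is what a reader relies on to judge how well it protects patients from a drug worse than history.

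**Working it through.** **Inputs from 7.2.** mS ~ IG(17.6, 131.2); mE ~ IG(3, 15.8); cutoff .07; accrual 2 per month; maximum 40. The historical 12-month RFS of .35 gives a rate of -ln(.35)/12 = .0875 per month and a median of .693/.0875 = 7.9 months, as stated. First dose is on day 42 to 100 after transplant (3.1.4.3.3).

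**Posterior.** With d events and T months of total follow-up, mE | data ~ IG(3 + d, b) with b = 15.8 + .693T. Pr(mS < mE | data) is the Beta(3 + d, 17.6) distribution function at b/(b + 131.2).

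**How the convention matters.** Take d = 5 and T = 20: b = 29.66, the argument is .184 and the probability is .068, so accrual stops. If one of the five events is still undetected (d = 4, T held at 20), the probability is .129 and accrual continues. If all five events are known but event-free time is cut back so that T = 14, then b = 25.50 and the probability is .036, further below the cutoff.

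**Reproducing the plan's table.** Every event is known on its date, TE runs from first dose, and the rule is checked at each enrolment (20,000 runs). Stop probabilities are .822/.343/.096/.027/.007, against .827/.339/.103/.036/.009 stated. Mean N is 21.9/32.5/37.6/39.2/39.8, against 21.8/32.5/37.3/39.0/39.7.

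**On the plan's schedule.** Four assumptions are not in the documents:
- A stated share of events is MRD-first.
- Each such event is recorded at the next scheduled marrow (day 100, 183 or 365), or 3 months after it occurs if that is sooner. All other events are recorded at once.
- First dose is uniform over days 42 to 100.
- Accrual is Poisson.

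| Event-free patients counted to | MRD-first share | .15 | .25 | .35 |
|---|---|---|---|---|
| Plan's table | not stated | .827 | .339 | .103 |
| Look date, dated at detection | 10% | .78 | .28 | .08 |
| Look date, dated at detection | 25% | .68 | .21 | .05 |
| Look date, dated at detection | 50% | .50 | .12 | .03 |
| Look date, back-dated to true date | 25% | .77 | .27 | .08 |
| Last marrow, dated at detection | 0% | .97 | .68 | .30 |
| Last marrow, dated at detection | 25% | .90 | .51 | .20 |
| Last marrow, dated at detection | 50% | .81 | .37 | .13 |

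The columns are true 1-year RFS. Without the 3-month surfacing, the look-date figures are .63/.20/.05 at 25% and .41/.10/.03 at 50%.

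**Allowing for delay in the historical figure.** Suppose recorded, not true, 12-month RFS is set to .15/.25/.35, as would apply if history carried the same delay. Look-date counting then gives .80/.31/.08 at a 10% share, .77/.28/.07 at 25% and .69/.20/.05 at 50%. At 25% the losses against the table are about 6, 6 and 3 points. Without the adjustment they are 15, 13 and 5 points (.827 - .68, .339 - .21, .103 - .05).

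**The case against.** Four points can be made for the plan.

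**The direction is not fixed.** A reader might infer that late detection always hides failures and so always makes the rule too lenient. The documents do not support that. Section 7.2 says only that TE may be right-censored, and counting to the last marrow usually gives over-stopping. Even that is not uniform. In a variant with no 3-month surfacing, where every event in the first year after transplant is found only at a marrow and dated there, last-marrow counting gives .356/.094/.027. This objection stands.

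**Immediate knowledge is not the only model close to the table.** In the same variant with half of events known at once, last-marrow counting gives .749/.324/.113/.038/.011, within 2 points of the table in four rows of five. The reproduction shows that immediate knowledge is sufficient for the published figures, not that it is the only route. This also stands.

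**The size rests on assumptions.** Neither the MRD-first share nor the 3-month surfacing is in the documents. Discretionary marrows under 4.2.3.4 could shorten delays, and the historical rate may carry a similar delay. The first is why a range is shown, and the second reduces the loss without removing it.

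**No marrow is shown to be missing.** If RFS ran from first dose, the 1-year marrow would fall 265 to 323 days later (365 - 100 and 365 - 42). That is before a 12-month landmark and before 12 cycles of 28 days (336 days), although treatment "will be continued until treatment failure or for a maximum of 12 cycles". A reader might infer that a 12-month marrow has been left out. But the plan never states that clock, and it counts both assessments and follow-up from transplant. On a transplant clock the 1-year marrow meets the 1-year landmark. What is missing is a stated time origin.

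**Conclusion.** The concern holds in limited form. The stop probabilities in 7.2 match a trial in which each event is known when it happens. With MRD counted as progression and tested on schedule only three times, they do not generally describe the rule the trial would run.

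At an assumed 25% MRD-first share, the probability of stopping a drug with true 1-year RFS of .25 is about .21 under one unstated convention and .51 under another, against .339 in the table. Back-dating events, or assuming that history has the same delay, brings the lower figure up to about .27 or .28.

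Neither the direction nor the size of the error can be settled from the documents, because the counting convention and the MRD-first share are both absent. A reader might also want to replace the .07 cutoff now. That is not supported, since any new value would suit only one convention and one assumed share. The historical .35 itself is not in question here.

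**What to change.** Amend 7.2 as follows.

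(a) State the time origin of TE. Timing from transplant with delayed entry at first dose puts the 1-year landmark on the 1-year marrow. Under the exponential model, each patient still contributes time only from first dose.

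(b) Date progression at the first positive test, and fix the date to which event-free patients are counted at each look. Where possible, use the same convention as the data behind the historical .35.

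(c) Rerun and restate the operating-characteristics table with MRD progression revealed at the scheduled marrows, over a stated range of MRD-first shares such as 0% to 50%. Reconsider the .07 cutoff only after seeing that rerun.

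The cost is one amendment and a simulation rerun, with no added patients, visits or marrows. The downside is that the restated stop probabilities may look less favourable than the present ones.
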